You may take your essential medications with a small amount of water but do not take anything that could affect your bowel (see previous list).

You may brush your teeth, but please try not to swallow any toothpaste.

If you are diabetic requiring insulin or diabetes medicine, please contact us for information about adjusting your morning dose.

What happens during the test?

At your appointment the physiologist will explain how the test works, what SIBO is and ask you to describe your symptoms. Please feel free to ask any questions you may have about the test procedure at this stage.

You will then be asked to give a baseline breath sample by blowing into a test tube through a straw.

The test substrate, which is a non-digestible sugar, will be mixed with water and given to you to drink.

Breath samples will then be collected every 15 minutes. During this time, you will be invited to sit in our waiting room which has wi-fi and television. Please do not eat, chew gum, smoke, sleep or exercise during your test. Throughout the test the physiologist will note any symptoms that occur.

The test will last 2 hours and 15 minutes.

You may return to your usual diet and activity after the test

Appendix 2

HYDROGEN & METHANE BREATH TEST PROTOCOL

PURPOSE

To provide guidelines for all staff assisting with or performing this procedure.

POLICY

Hydrogen & Methane Breath Testing

PROCEDURE

INDICATIONS:

1. Investigation of Small Intestinal Bacterial Overgrowth
2. Investigation of Colonic Dysbiosis

ABSOLUTE CONTRAINDICATIONS

1. Post-prandial hypoglycaemia
2. Failure to give consent

RELATIVE CONTRAINDICATIONS

1. Failure of patient to follow pre-study diet
2. Non-adherence to cessation of smoking
3. Failure of patient to fast for 12 hours prior to the study
4. Antibiotic therapy in the previous 4 weeks

EQUIPMENT

- Functional Gut Diagnostics Breath Test Kit containing
 - 10 collection tubes
 - 10 collection tube labels
 - 1 straw
 - 1 substrate sachet (lactulose/glucose/lactose/fructose)
 - 2 bubble wrap pouches
 - Symptoms score sheet
- Consent form and clinical history sheet
- Plastic cups
- Drinking water

Before the procedure

- Check the patient details including a contact telephone number

- Obtain the patient's history using the clinical history sheet. This should include: symptoms, duration, previous medical and surgical history, medication, previous treatments/diagnostic procedures and any known allergies
- Confirm the patient has stopped required medication, followed the pre-study diet and fasted for the past 12 hours.
- Explain the test procedure, benefits and risk of the test and obtain written consent using the consent form.

Procedure Method

- Collect a baseline breath sample by asking the patient to insert the straw halfway into the tube and breath through the straw until they see condensation. They can then remove the straw and replace the cap.
- Ensure to fill out all the information on the collection tube label and adhere to each tube after sample collection.
- Ask the patient if they are experiencing any symptoms (specifically bloating, nausea or abdominal pain) at the beginning of the test. Ask them to rate each symptom on a scale of 0 – 10 (with 0 being no symptoms and 10 being severe symptoms) and record the results on the symptom score sheet.
- Mix the substrate sachet with 200ml drinking water and instruct the patient to drink it.
- Continue to take samples and note symptoms every 15 minutes until 10 samples have been collected (full test duration is 2 hours and 15 minutes). Invite the patient to sit in the waiting room for the rest of their test.
- When collecting the 10th sample, invite the patient back into the clinic room and explain that results will be sent out electronically to the referring doctor in 48 hours.
- Ask if they have any questions

After the procedure

- Ensure all 10 collection tubes are labelled correctly and pack them into the bubble wrap pouches. Put the pouches and the symptom sheet back into the kit box and post back to Functional Gut Diagnostics.
- Dispose of the plastic cup and straw.

Reporting the results

- Once the Functional Gut Diagnostics technical report is uploaded to DGL, an TFGC cover letter will be written using the report template. This will be saved and sent as a PDF file.
- Templates are available on each TFGC laptop/ computer on the desktop and have been emailed to each member of staff at TFGC.

Clinic risk assessment

- A clinical risk assessment has been made regarding this procedure which is available as a hard copy in the Clinic Registry folder and has been emailed to each member of staff at TFGC.

How the results will be communicated?

- If the patient consents, during the consent process, to allowing TFGC to email reports to the referring consultant then this will be the only option.

- If the referrer or patient requests another method then the use of fax will be used.
- TFGC is a diagnostic clinic and all reports/results will be sent to the referring consultant.

Appendix 3 – Reflux Questionnaire

Reflux Questionnaire

Patient Name:

Date:

GERD-HRQL Questionnaire

On PPIs Off PPIs If off, for how long? _____ days/weeks/months

Scale:

0 = No symptom

1 = Symptoms noticeable but not bothersome

2 = Symptoms noticeable but not bothersome everyday

3 = Symptoms bothersome everyday

4 = Symptoms affect daily activity

5 = Symptoms are incapacitating

Please check the box to the right of each question to best describe your experience over the past 2 weeks;

- | | | | | | | |
|---|----------------------------|----------------------------|----------------------------|----------------------------|----------------------------|----------------------------|
| 1. How bad is the heartburn? |  0 |  1 |  2 |  3 |  4 |  5 |
| 2. How is the heartburn when lying down? |  0 |  1 |  2 |  3 |  4 |  5 |
| 3. How bad is the heartburn when standing up? |  0 |  1 |  2 |  3 |  4 |  5 |
| 4. Heartburn after meals? |  0 |  1 |  2 |  3 |  4 |  5 |
| 5. Does heartburn change your diet? |  0 |  1 |  2 |  3 |  4 |  5 |
| 6. Does heartburn wake you from sleep? |  0 |  1 |  2 |  3 |  4 |  5 |

Heartburn score =

- | | | | | | | |
|---|----------------------------|----------------------------|----------------------------|----------------------------|----------------------------|----------------------------|
| 7. How bad is the regurgitation? |  0 |  1 |  2 |  3 |  4 |  5 |
| 8. Regurgitation when lying down? |  0 |  1 |  2 |  3 |  4 |  5 |
| 9. Regurgitation when standing up? |  0 |  1 |  2 |  3 |  4 |  5 |
| 10. Regurgitation after meals? |  0 |  1 |  2 |  3 |  4 |  5 |
| 11. Does regurgitation change your diet? |  0 |  1 |  2 |  3 |  4 |  5 |
| 12. Does regurgitation wake you from sleep? |  0 |  1 |  2 |  3 |  4 |  5 |

Regurgitation score =

- | | | | | | | |
|--|----------------------------|----------------------------|----------------------------|----------------------------|----------------------------|----------------------------|
| 13. Do you have difficulty swallowing? |  0 |  1 |  2 |  3 |  4 |  5 |
|--|----------------------------|----------------------------|----------------------------|----------------------------|----------------------------|----------------------------|

0 1 2 3 4 5

0 1 2 3 4 5

14. Do you have pain with swallowing?
15. If you take medication, does this affect your daily life?
16. How satisfied are you with your present condition?
 Satisfied Neutral Dissatisfied

Total score (inc. heartburn and regurgitation scores) =

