Participants will visit The Functional Gut Clinic (FGC) to carry out a repeat HMBT following FGC protocol (appendix 2). Participants will also be asked to repeat the Reflux questionnaire (appendix 3), IBS-SSS questionnaire (appendix 4) and bowel habit questionnaire (appendix 5). Completion of the repeat breath test and questionnaires will mark the end of the study for the patient.

Eligibility

Inclusion Criteria

1. Participant has provided written informed consent before participating in the study after being given a full description of the study and prior to any study-specific procedures being performed.
2. Patient has been taking PPI therapy for >6 months
3. Patient reports bloating ≥ 3 on screening questionnaire
4. Patient reports one of the following ≥ 3 on screening questionnaire - belching, heartburn, nausea, reflux sensation
5. Participant is a male or non-pregnant female and is age 18 years of age or above
6. Participant is able to communicate well with the Investigator and to comply with the requirements for the entire study.
7. Patient has capacity to understand written English
8. Patient agrees to follow pre-test diet for 24 hours before giving test sample (Appendix A).
9. Participant agrees to refrain from strenuous physical activity on the day of the breath test.
10. Participant agrees to refrain from smoking on the day of the breath test
11. Participant agrees to an overnight fast on the night before the breath test. Food and drink must be withheld until after all breath test samples have been taken.
12. Participant agrees to not take any probiotic for 7 days before the breath test.
13. Participant has a body mass index (BMI) between 18.5 and 34.9kg/m² (bounds included).

Exclusion criteria

1. Participant reports using any prohibited medication, medical device or supplementation
2. Participant has taken antibiotics or undergone colonoscopy/sigmoidoscopy in the 4 weeks prior to enrolment.
3. Participant has a diagnosis of any organic gastrointestinal disease, including inflammatory bowel disease, coeliac disease and diverticulitis.
4. Participant has known mechanical obstruction of the GI tract
5. Participant has diabetes
6. Participant has any hepatic disease
7. Participant has any disease of the CNS
8. Participant is involved in this study as an Investigator, sub-Investigator, study coordinator, other study staff, or Sponsor member.

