9. Participant has had previous abdominal or colorectal surgery except appendectomy, cholecystectomy, or hysterectomy.
10. Participant has previously taken Silicolgel in the past month
11. Participant has a known hypersensitivity to any of the ingredients of Silicolgel
12. Participant suffers regularly from constipation

13. Participant is involved in any other research projects either currently or during the previous month

Test Product, Planned Doses, Mode of Administration and duration of treatment

Silicolgel 15ml, oral administration. Total Participation is expected to last 12 days, with a 10-day treatment period. During the treatment period participants will take 15ml Silicolgel three times daily. Silicolgel should be taken one hour before meals. Silicolgel may be taken undiluted or diluted with water. Due to its inability to be absorbed into the blood stream and physical not pharmacological mechanism, Silicolgel is considered a class IIa medical device according to the Medical Device Directive 93/42/EEC Annex rule 5.

The bottle must be shaken before each administration. The bottle of Silicolgel should be stored above 2°C. After opening the bottle, the product should be consumed within 3 months, and it should not be used after the date given on the label.

Blinding procedure

All participants will be blinded to the study device. Silicolgel bottles will be labelled without any Silicolgel branding or product ingredients. Study participants will be made aware that the product is a CE marked medical device that works via intestinal adsorption. Any potential side effects of the product will also be disclosed to the patient.

Study Outcome Assessments

Primary outcome assessment

Mean change in cumulative total breath hydrogen and methane, will be determined from baseline HMBT to end of study HMBT. Cumulative total hydrogen and cumulative total methane will be calculated independently of one each other. Breath hydrogen and breath methane will be measured in units of parts per million (ppm). Statistical significance will be determined using a paired t-test ($p < 0.05$).

Each HMBT samples will be analysed using gas chromatography analysis on the day of the breath test being carried out. Breath carbon dioxide will also be measured in order to verify the validity of each sample and apply a correction factor. A correction factor above 2.5 ($CO_2 < 2\%$) is considered an invalid sample.

Secondary outcome assessment

Reflux Questionnaire (Appendix 3)

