The Reflux Questionnaire is a validated questionnaire that will be used to determine severity of upper GI symptoms. The questionnaire is made up of 16 questions, each scored 0 to 5. The total of these 16 questions will be calculated to determine symptom severity. Mean difference in scores from baseline reflux questionnaire and end of study reflux questionnaire will be determined using a paired t-test, to determine significance ($p < 0.05$).

Irritable Bowel Syndrome Symptom Severity Score (IBS-SSS) (Appendix 4)

The IBS-SSS is a validated questionnaire that will be used to determine severity of abdominal and bowel symptoms. The questionnaire is comprised of 7 questions, 5 of which are scored from 0 to 10. The total of these 5 questions will be calculated and multiplied by 10 to determine symptom severity. Mean difference in scores from baseline IBS-SSS and end of study IBS-SSS will be determined using a paired t-test, to determine significance ($p < 0.05$).

Bristol stool chart (Appendix 5)

The Bristol stool chart will be used by participants stool frequency and consistency. Participants will be asked to identify their stool type during the past 7 days using the chart and describe their stool frequency. Mean difference in stool frequency and consistency from baseline and end of study will be determined using a paired t-test, to determine significance ($p < 0.05$).

Safety Outcome Assessments

Definitions

Types of AEs associated with medical devices and applicable for this study are defined in accordance with the European Commission guidelines on medical devices.

Adverse events

Any untoward medical occurrence, unintended disease or injury or any untoward clinical signs (including an abnormal laboratory finding) in subjects, users or other persons whether or not related to the investigational medical device.

NOTE 1: This includes events related to the procedures involved (any procedure in the clinical investigation plan).

NOTE2: For users or other persons this is restricted to events related to the investigational medical device.

Adverse Device Effect (ADE)

AE related to the use of an investigational medical device.

NOTE 1: This includes any AE resulting from insufficiencies or inadequacies in the instructions for use, the deployment, the implantation, the installation, the operation, or any malfunction of the investigational medical device.

NOTE 2: This includes any event that is a result of a use error or intentional misuse

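### Levels 1 and 2 of the reflux response scale overlap as printed, which adds noise to the change in the reflux total; item 15 does not say whether the study product counts as medication.

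*Combined protocol and SAP*

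**What the plan says.** The Secondary outcome assessment section introduces the form thus: "The Reflux Questionnaire is a validated questionnaire that will be used to determine severity of upper GI symptoms". The item scores are summed, and the change from Day 1 to Day 12 is tested with a two-tailed paired t-test at p < 0.05. There are 20 participants and no control arm.

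The scale in Appendix 3 is printed once, above all the items. Three of its six levels matter here:

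- Level 1: "1 = Symptoms noticeable but not bothersome"
- Level 2: "2 = Symptoms noticeable but not bothersome everyday"
- Level 3: "3 = Symptoms bothersome everyday"

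Item 15 on the same form is "15. If you take medication, does this affect your daily life". The form does not define medication. An inclusion criterion is "Patient has been taking PPI therapy for >6 months", and the form opens by asking whether the respondent is on or off PPIs. The product taken from Day 2 to Day 11 is classed as a device: "Silicolgel is considered a class IIa medical device according to the Medical Device Directive 93/42/EEC Annex rule 5". The Blinding procedure section adds: "Study participants will be made aware that the product is a CE marked medical device that works via intestinal adsorption".

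**The concern.** Response levels should be mutually exclusive, and these two are not. Level 2 is level 1 with one word added, so a participant who notices a symptom but is never bothered by it can tick either box truthfully. A different choice on Day 12 from Day 1 moves that item by one point with no change in reflux.

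The affected range may well be used. Everyone is on long-term PPI therapy, and under Eligibility a participant can qualify on bloating plus belching or nausea. The form has no item on belching or nausea, so some participants may have only mild heartburn or regurgitation.

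Item 15 raises a different question. On Day 1 no study product has been taken. By Day 12 the participant has taken an oral liquid three times a day before meals for ten days. Nothing on the form or in the visit instructions says whether item 15 covers it. If some participants include it only on the second form, the total picks up the burden of the regimen as well as reflux.

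What is at stake is the precision of one tested secondary outcome and, for item 15, a possible shift against the product. The primary breath-gas outcome is not affected.

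**Working it through.** **The plan's own figure.** The sample size of 20 is set because this is a pilot. The documents give no effect size, SD or power, so there is nothing to reproduce. The SDs of change, switching probabilities and item 15 shifts below are assumptions.

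**Inputs from the documents.** n = 20; two-sided paired t-test at 0.05; items 1 to 14 are symptom items scored 0 to 5; item 15 is also scored 0 to 5; item 16 has three satisfaction categories. The maximum is 15 × 5 = 75 as the form is printed, or 16 × 5 = 80 by the protocol text. That mismatch is a separate matter and does not affect this check.

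**Step 1: noise from the overlap.** Let m items sit at the level 1/2 boundary at both visits with no true change. Let each answer be level 2 with probability q, independently by item and visit. The mean change is then zero, and the added SD of the change is √(m × 2 × q(1 − q)).

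| m | q = 0.1 | q = 0.5 |
|---|---|---|
| 5 | 0.95 | √2.5 = 1.58 |
| 10 | 1.34 | √5 = 2.24 |
| 14 | 1.59 | √7 = 2.65 |

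**Step 2: type I error.** In 40,000 simulated trials of 20 people whose change consisted only of this switching, the paired t-test rejected in 5.07% (m = 5, q = 0.5), 4.99% (m = 14, q = 0.5) and 5.12% (m = 14, q = 0.1). The test keeps its nominal level.

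**Step 3: power.** With n = 20, a standardised effect of 0.66 gives 80% power (noncentral t). Add the largest noise in the table, variance 7, to an assumed SD of change:

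- SD 5: √(25 + 7) = 5.66. The effect becomes 0.66 × 5/5.66 = 0.58, and power is 70%.
- SD 8: √(64 + 7) = 8.43. Power is 76%.
- SD 10: √(100 + 7) = 10.34. Power is 77%.
- SD 12: √(144 + 7) = 12.29. The effect becomes 0.66 × 12/12.29 = 0.64, and power is 78%.

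**Step 4: item 15.** If some participants count the burden of the product on Day 12 only, the mean change shifts upward. With no change in reflux, the probability of a significant result is:

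| Mean shift | SD of change 5 | SD of change 12 |
|---|---|---|
| 0.5 points | 0.071 | 0.054 |
| 1 point | 0.136 | 0.064 |
| 2 points | 0.397 | 0.109 |

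A mean shift of 1 point needs, for example, half the participants to move by 2 points (10 × 2/20 = 1). Higher scores are worse, so the shift is towards apparent worsening and subtracts from any real improvement.

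**The case against.** The strongest reply is that the comparison is within person on an identical form. A participant who reads level 2 the same way on both days contributes no error, and symmetric switching leaves the expected change at zero. That stands, and it limits the overlap to a loss of precision. It is also fair that this is a secondary outcome in a 20-person pilot that makes no power claim.

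The instrument is described as validated, and the source is not available here. Whether level 2 is a copying slip or the instrument's own wording cannot be settled from the documents. Rewriting a validated form carries its own cost, so the remedy has to depend on a check.

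Three stronger readings are tempting, and the documents do not support them:

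- **That item 15 changes meaning once the product starts.** Every participant already takes a PPI, the form opens with PPI status, and participants are told that the product is a medical device. The concomitant treatment section also names medicines and devices as distinct categories. The documents show only that the term is undefined and may be read differently on Day 12.
- **That the total could swing by 15 points, or that the added SD is 3.5 to 7.1 points.** The first needs all 15 scored items at the boundary and all moving the same way. The second assumes that each person decides afresh, by coin toss at each visit, how to read the whole scale (m × √0.5 = 3.5 for 5 items, 7.1 for 10). One scale printed above all items makes a form-wide reading possible, but nothing suggests that it would be redrawn between visits.
- **That the overlap produces a false improvement through expectation.** An expectation-driven move from 2 to 1 is possible. But expectation can affect any self-reported score in an uncontrolled, open-label design, and clearer wording would not remove it.

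**Conclusion.** The overlap between levels 1 and 2 is real as printed and sits on a form that feeds a tested outcome. Its likely effect is extra noise. Under independent switching at probability 0.5, the added SD of change runs from about 1.6 points (5 items) to 2.6 points (14 items). The largest case costs between 2 and 10 percentage points from 80% power over assumed SDs of change of 12 down to 5. If switching is rarer or readings are stable, the loss is smaller. Bias in the mean change would need readings to drift in one direction, which the documents do not show.

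The undefined term in item 15 is a lesser, conditional point. If product burden is counted on Day 12 only, scores rise and benefit is masked. How many participants would do this is unknown.

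**What to change.** 1. Before first use, check level 2 against the source instrument. If it is a transcription error, restore the source wording so that levels 1 and 2 exclude each other. If the source has the same wording, leave the validated form as it is and note the overlap as a limitation of the reflux total.
2. Do not alter item 15. Pre-specify one sensitivity analysis: either the heartburn and regurgitation subscores already on the form (items 1 to 6 and 7 to 12), or the total without item 15. Either removes item 15 from the comparison. Neither cures the overlap, which runs through the remaining items.

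The cost is one form check and one extra line of analysis.

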Appendix 4 – Irritable Bowel Syndrome Symptom Severity Score (IBS-SSS)

IRRITABLE BOWEL SYNDROME SYMPTOM SEVERITY SCORE (IBS-SSS)

1. A. Do you currently (in the last month) suffer from abdominal (tummy) pain?
- Yes
- No
- B. If yes, how severe is your abdominal (tummy) pain? Please indicate a number from 0 to 10, with 0 meaning "no pain" and 10 meaning "very severe."
- no pain 0 1 2 3 4 5 6 7 8 9 10 very severe
- C. Please enter the number of times that you get the pain every 10 days. For example, if you choose 4 it means that you get pain 4 out of 10 days. If you get pain every day enter 10.
- no days with pain 0 1 2 3 4 5 6 7 8 9 10 10 days with pain
2. A. Do you currently suffer from abdominal distention *(bloating, swollen or tight tummy)? *Women, please ignore distention related to your period.
- Yes
- No
- B. If yes, how severe is your abdominal distention/tightness? Please indicate a number from 0 to 10, with 0 meaning "no distention" and 10 meaning "very severe."
- no distention 0 1 2 3 4 5 6 7 8 9 10 very severe
3. How dissatisfied are you with your bowel habits? Please indicate a number from 0 to 10, with 0 meaning "very happy" and 10 meaning "very unhappy."
- very happy 0 1 2 3 4 5 6 7 8 9 10 very unhappy
4. Please indicate how much abdominal pain or discomfort or altered bowel habits are affecting or interfering with your life in general. Please indicate a number from 0 to 10, with 0 meaning "not at all" and 10 meaning "completely."
- not at all 0 1 2 3 4 5 6 7 8 9 10 completely

Total x10 = Score =

Bristol Stool Chart

Type 1		Separate hard lumps, like nuts (hard to pass)
Type 2		Sausage-shaped but lumpy
Type 3		Like a sausage but with cracks on its surface
Type 4		Like a sausage or snake, smooth and soft
Type 5		Soft blobs with clear-cut edges (passed easily)
Type 6		Fluffy pieces with ragged edges, a mushy stool
Type 7		Watery, no solid pieces. Entirely Liquid

1) Over the last 7 days, how would you describe the frequency of your bowel movements?

- More than 3 a day
- 1-3 a day
- 3-6 a week
- Less than 3 a week

2) Using the Bristol Stool Chart above, how would you describe your average bowel movement over the last 7 days?

- Type 1 Type 2 Type 3 Type 4 Type 5 Type 6 Type 7
